8.5. Pharmacokinetics

Pharmacokinetic parameters are not evaluated in this study.

8.6. Genetics

Genetic analyses will not be collected in this study.

8.7. Biomarkers

Biomarkers are not evaluated in this study.

8.8. Immunogenicity Assessments

Immunogenicity assessments are not included in this study.

8.9. Health Economics

Health economics/medical resource utilization and health economics parameters are not evaluated in this study.

9. STATISTICAL CONSIDERATIONS

Detailed methodology for summary and statistical analyses of the data collected in this study is outlined here and further detailed in the SAP, which will be maintained by the sponsor. The SAP may modify what is outlined in the protocol where appropriate; however, any major modifications of the primary endpoint definitions will also be reflected in a protocol amendment. Data from Part 1 and Part 2 of the study will not be pooled.

9.1. Statistical Hypothesis

Part 1 of this study is an estimation study with the objective to estimate the IGA response rates of the treatment groups (Etrasimod 2 mg QD and Placebo) as well as the IGA response rate difference between the treatment groups at Week 16. There are no statistical hypotheses in this study. The sample size calculation considers only the precision of the estimation of IGA response rates and the treatment difference in response rate (Section 9.5).

9.1.1. Estimands

9.1.1.1. Primary Estimand

The primary estimand (E1) is defined by the following attributes:

- 1. Treatment condition: received study intervention of etrasimod 2 mg QD or placebo.
- 2. Population: Participants with moderate-to-severe AD as defined by the inclusion and exclusion criteria.
- 3. Variables: Proportion of participants achieving IGA score of clear (0) or almost clear (1) and a reduction from baseline of ≥2 points at Week 16. A participant who experiences an intercurrent event of initiation of prohibited medications or discontinuation of study treatment due to any reason (whichever is earlier), will be considered an IGA non-responder (ie, treatment failure) at Week 16.

4. Intercurrent Events:

- A) Initiation of prohibited medications a participant who receives prohibited medication post-randomization prior to the Week 16 visit will be considered an IGA non-responder (ie, treatment failure) at Week 16.
- B) Discontinuation of study intervention due to any reason prior to the Week 16 visit a participant who discontinues study intervention due to any reason will be considered an IGA non-responder (ie, treatment failure) at Week 16.
- 5. Population level summary: The difference in IGA response rates at Week 16 between etrasimod 2 mg QD and placebo.

Estimand E1 will be similarly applied to the binary secondary endpoint (ie, EASI-75 at Week 16) as well as the binary exploratory endpoints (eg, ≥4-point reduction from baseline in PP-NRS score at Week 16) with the endpoint substituted appropriately.

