6.9.2. Prior Treatments

Table 1. Prohibited Medication or Procedure Washout Periods Prior to Day 1

Time Frame	Therapies	
Any time prior to Randomization	S1P receptor modulators (eg, fingolimod, siponimod, ozanimod), α4β1 integrin receptor antagonist (eg, natalizumab)	
Within 24 weeks	Anti-CD20 antibodies (eg, rituximab, ocrelizumab), anti CD52 antibodies (eg, alemtuzumab), other cell depleting therapies (eg, bone marrow transplantation, total body irradiation)	
Within 8 weeks (or 5 half-lives if shorter)	Any biologic treatment other than already listed, eg, anti-IL4/13 antibodies (eg, dupilumab), anti-IL13 antibodies (eg, tralokinumab, lebrikizumab), anti-IL-17 antibodies (eg, secukinumab), anti-IL-12/23 antibodies (eg, ustekinumab), anti-IL-31 antibodies (eg, nemolizumab), anti-IL-23 antibodies (eg, risankizumab)	
Within 6 weeks	Live-attenuated replication-competent vaccines are prohibited	
Within 4 weeks (or 5 half-lives if shorter)	Any investigational therapy other than the study treatment, unless therapy belongs to a drug category described above which requires a longer washout period, in which case the longer washout period should be used.	

Table 1. Prohibited Medication or Procedure Washout Periods Prior to Day 1

Time Frame	Therapies	
Within 4 weeks	Any other systemic treatment intended for AD (eg, azathioprine, methotrexate, cyclosporine, mycophenolate, PDE-4 inhibitors, and systemic glucocorticoids)	
	Note: corticosteroid intranasal sprays and/or corticosteroid inhalers are allowed for participants with stable asthma. Ophthalmic and ear drop corticosteroids are also allowed.	
	Topical and systemic JAK inhibitors (eg, baricitinib, abrocitinib, upadacitinib, ruxolitinib, delgocitinib, tofacitinib)	
	Any IV medications taken in response to serious infection that require hospitalization or treatment	
	Moderate or strong inhibitors or inducers that inhibit or induce at least 2 of the following: cytochrome P450 (CYP)2C8, CYP2C9, and CYP3A4 (e.g., fluconazole, rifampin, enzalutamide)	
	Phototherapy for AD or artificial tanning (beds, booths, or lamps), including psoralen and ultraviolet A, ultraviolet B, tanning booth, and excimer laser	
Within 1 week Topical treatments that could affect AD disease and/or evaluate (eg, crisaborole, corticosteroids, calcineurin inhibitors [eg, tacr pimecrolimus], tars, antibiotic creams, topical antihistamines).		

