- Systemic immunosuppressive/immunomodulating drugs (eg, cyclosporine, azathioprine, methotrexate), including topical or oral JAK inhibitors (requires permanent discontinuation of study treatment but participants are not required to withdraw from the study).
- Any biologic treatment, anti-IL4/13 antibodies (eg, dupilumab), anti-IL13 antibodies (eg, tralokinumab, lebrikizumab), anti-IL17A antibodies (eg, secukinumab), anti-IL12/23 antibodies (eg, ustekinumab), anti-IL31 antibodies (eg, nemolizumab), anti-IL23 antibodies (eg, risankizumab) requires permanent discontinuation of study treatment, but participants are not required to withdraw from the study.
- Any IV medications taken in response to serious infection that required hospitalization or treatment.

- Moderate/strong inhibitors or inducers that inhibit or induce at least 2 of the following: cytochrome P450 (CYP)2C8, CYP2C9, and CYP3A4 (e.g., fluconazole, rifampin, enzalutamide, Section 10.8.1).
- Live-attenuated replication-competent vaccines starting 6 weeks prior to baseline (Day 1), during study treatment and for 4 weeks after the last dose of study treatment.
- Start, stop, or change in dosage of any anti-arrhythmic drugs (Class I to IV) within 1 week before or after treatment initiation or reinitiation following dose interruption of a duration requiring in-clinic cardiac monitoring (Section 6.1.1).
- Any investigational drug other than the study treatment.

Participants who complete the treatment period no longer need to abstain from the medications that were prohibited during the treatment periods, unless noted otherwise (eg, live attenuated vaccines for 4 weeks after the last dose of study treatment).

For prohibited concomitant procedures:

- Participants may not undergo phototherapy for AD or artificial tanning (beds, booths, or lamps), including psoralen and ultraviolet A, ultraviolet B, tanning booth, and excimer laser.
- Participants should not take bleach baths.
- Participants should not undergo cell depleting therapies (eg, bone marrow transplantation, total body irradiation).
- Participants should not undergo major elective surgery while on study treatment.
- Participants may not donate blood during the study and for 30 days after the last dose of study treatment.
- Participants may not donate sperm, or oocytes during the study and for 28 days after the last dose of study treatment.

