2.2.1. Primary Estimand

There are two intercurrent events considered for Part 1 DB phase of this study, (1) the initiation of prohibited medications, and (2) the discontinuation of the study treatment (etrasimod or placebo) due to any reason. Estimand E1 is an estimand strategy for a binary endpoint at a visit, when applied to the primary endpoint of IGA response at Week 16, it is known as the primary estimand. Estimand E1 is illustrated using the primary endpoint below.

Estimand E1 for a binary endpoint at a visit:

Estimand E1 uses a composite strategy and estimates the treatment effect at a visit considering a participant as non-responder after experiencing the intercurrent event of initiation of prohibited medications or discontinuation of study treatment. The primary estimand is Estimand E1 applied to the primary endpoint of IGA response at Week 16, and is defined according to the primary objective. The primary estimand is defined by the following five attributes:

- 1. Treatment condition: received study intervention of etrasimod 2 mg QD or placebo.
- 2. Population: Participants with moderate-to-severe AD as defined by the inclusion and exclusion criteria.
- 3. Variable: IGA response at Week 16 is score of clear (0) or almost clear (1) and a reduction from baseline of ≥2 points. A participant who experiences the intercurrent event of initiation of prohibited medications or discontinuation of study treatment due to any reason (whichever is earlier), will be considered an IGA non-responder (ie, treatment failure) at Week 16.

4. Intercurrent events:

- Initiation of prohibited medications a participant who receives prohibited medications post-randomization prior to the Week 16 visit will be considered an IGA non-responder (ie, treatment failure) at Week 16.
- Discontinuation of study intervention due to any reason prior to the Week 16 visit

 a participant who discontinues study treatment due to any reason will be
 considered an IGA non-responder (ie, treatment failure) at Week 16.
- 5. Population-level summary: The difference in IGA response rates at Week 16 between etrasimod 2 mg QD and placebo.

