Appendix 4. Initiation of Prohibited Medications

The intercurrent event of initiation of prohibited medications will be identified using the final reconciliated PIPD dataset. The PD category of "concomitant medications" and the subcategory of "took prohibited concomitant medication/vaccine – meeting intercurrent event" will be used to identify this protocol deviation as the intercurrent event. This protocol deviation has to be verified using participant's entries of concomitant medications via clinical review. Once verified, the analysis population exclusion (APE) status will be checked "Yes" and this protocol deviation is deemed to be the intercurrent event of initiation of prohibited medications. The onset date of the protocol deviation as recorded on the PIPD dataset will DMB02-GSOP-RF02 7.0 Statistical Analysis Plan Template 31-Jan-2022

serve as the date of initiation of prohibited medications. This is applicable to the Part 1 DB phase only.

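### Intercurrent event 1 expressly covers only prohibited medications, so a participant who has prohibited phototherapy and stays on study drug can be scored as a Week 16 responder

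*Protocol*

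**What the plan says.** SAP 2.2.1 is explicit about the number of events: "There are two intercurrent events considered for Part 1 DB phase of this study". The first is starting a prohibited medication. Protocol 9.1.1.1 gives the consequence: "a participant who receives prohibited medication post-randomization prior to the Week 16 visit will be considered an IGA non-responder". The second is stopping study treatment: "a participant who discontinues study intervention due to any reason will be considered an IGA non-responder". Protocol 9.1.1.2 and SAP 2.2.2 use the same two events for E2, where later data are set to missing and imputed.

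Protocol 6.9.3 gives two lists of prohibited medications. One requires study drug to be stopped permanently; the other does not. A third list follows under its own lead-in, "For prohibited concomitant procedures". Its first item reads "Participants may not undergo phototherapy for AD or artificial tanning". Bleach baths are on the same list. No stop of study drug is attached to either.

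Table 1 in Protocol 6.9.2 puts this entry among the therapies barred within 4 weeks before Day 1: "Phototherapy for AD or artificial tanning (beds, booths, or lamps), including psoralen and ultraviolet A, ultraviolet B, tanning booth, and excimer laser".

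SAP Appendix 4 identifies the first event from the protocol deviation data, using the concomitant medications category and the sub-category "took prohibited concomitant medication/vaccine – meeting intercurrent event". Each case is checked against the participant's concomitant medication entries. SAP 6.4.4 treats non-drug treatments as a class of their own and only summarises them.

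**The concern.** E1 uses a composite strategy: a participant who turns to other prohibited treatment should not be credited with a response. Phototherapy given for AD is such a treatment by the protocol's own account. It is prohibited, it is described as being for AD, and it has the same 4-week washout as systemic AD drugs such as methotrexate and cyclosporine. The estimand carries over only the medication half of the prohibition.

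The outcome is uneven. A short course of topical corticosteroid is a prohibited medication that does not require study drug to stop, so it falls within the wording of event 1. Phototherapy for AD does not.

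At stake is the Week 16 IGA response difference, the EASI-75 difference and the mean percent change in EASI. These results inform the decision on starting Part 2 (Protocol 4.1 and 9.4). No rescue is allowed during the 16 double-blind weeks, in a population that has already failed systemic therapy, so outside treatment for AD is a foreseeable deviation.

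**Working it through.** **Tracing one participant through the plan.** Take a participant who has phototherapy for AD before Week 16, stays on study drug and takes no prohibited medication.

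1. Event 1 (Protocol 9.1.1.1; SAP 2.2.1): the text requires a prohibited medication. Phototherapy is listed as a procedure, so the event is not met on its wording.
2. Flagging (SAP Appendix 4): the sub-category names medication and vaccine, and the check uses concomitant medication entries. Procedure entries are not mentioned.
3. Event 2: not met, because study drug continues and Protocol 6.9.3 does not require it to stop.
4. Data kept (SAP Appendix 3, Table 14): with no event flagged, all of the participant's data are used for E1 and E2.
5. Result: an IGA of 0 or 1 with a fall of at least 2 points is scored as a response, EASI-75 is scored in the same way, and the observed EASI value goes into the E2 model unchanged.
6. Other planned analyses: E1a and E2a are treatment-policy estimands and keep the data too. Protocol 9.2 defines only the full and safety analysis sets. No planned analysis removes the response.

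**The plan's own precision (Protocol 9.5).** Inputs: 30 per arm, 9% on placebo, 39% on etrasimod, two-sided 95% interval, normal approximation.

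- Placebo: 1.96 × √(0.09 × 0.91 / 30) = 10.24 points.
- Etrasimod: 1.96 × √(0.39 × 0.61 / 30) = 17.45 points, matching the stated bound of 17.5.
- Difference: 1.96 × √(0.09 × 0.91 / 30 + 0.39 × 0.61 / 30) = 20.24 points, matching the stated 20.2.

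The gap is one of definition and leaves these planning figures unchanged.

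**Size per participant.** One responder in an arm of 30 is 1/30 = 3.33 points on that arm's rate and on the difference. The planned CMH estimate gives the same 1/30 when the arms are balanced within each IGA stratum and the SAP's adjustment for 0% or 100% response is not triggered.

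Suppose the planning rates are what E1 would show with phototherapy counted as an event. Responders who slip through then give:

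| Extra responders after phototherapy | Placebo | Etrasimod | Difference |
|---|---|---|---|
| None | 9.0% | 39.0% | 30.0 |
| 1 on placebo | 12.3% | 39.0% | 26.7 |
| 2 on placebo | 15.7% | 39.0% | 23.3 |
| 1 on etrasimod | 9.0% | 42.3% | 33.3 |
| 2 on etrasimod | 9.0% | 45.7% | 36.7 |
| 1 on each | 12.3% | 42.3% | 30.0 |

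Two in one arm move the difference by 6.7 points, and 6.7 / 20.2 = 0.33 of the half-width. The range of 0 to 2 per arm is an assumption; the documents give no rate of use.

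**The case against.** The strongest reply is that the gap is narrow and its effect may be nil. Several things must happen together: phototherapy is used, study drug continues, and the participant reaches IGA 0 or 1 in refractory disease. Protocol 7.1 lists protocol deviation and physician decision among the reasons for stopping study drug, and a participant stopped for either becomes a non-responder through event 2. Cases would also be visible: Protocol 6.9 requires all procedures to be recorded, SAP 6.4.4 summarises non-drug treatments by arm, and SAP 6.5.6 lists all deviations. Part 1 is an estimation study without hypotheses, and even two cases stay well inside the half-width. All of this stands, and it limits the size. It does not close the gap, because stopping is discretionary and a listing does not change the estimate.

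Four stronger readings might be inferred, and the documents do not support them:

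- **That a procedure could never be flagged.** The coding rules for deviations are not in the documents, and the psoralen in PUVA might be entered as a medication. The line between classes is also not clean: total body irradiation appears in both a medication list and the procedures list. What can be said is that phototherapy is not expressly included.
- **That bleach baths are an equal case.** They are prohibited, but Table 1 sets no washout and no reason or effect on AD is stated.
- **That the coding is arbitrary because a vaccine can count and phototherapy cannot.** Live vaccines are on the list that requires study drug to stop, so event 2 would catch them anyway.
- **That the gap favours etrasimod or defeats the composite strategy.** No usage rate by arm is given. If use were higher on placebo, the difference would shrink. The strategy still works for the prohibited medications and for every discontinuation.

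**Conclusion.** The point holds as a gap in the definition. As written, E1 and E2 do not expressly treat phototherapy or artificial UV as an intercurrent event, although the protocol prohibits both and sets a washout for them. A participant who has either and stays on study drug can be counted as a Week 16 responder, and no planned analysis corrects this.

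Each such responder is worth 3.3 points on an arm's rate and on the difference, on the assumption of 30 per arm and balance within strata. The direction depends on the arm. Frequency is unknown and may be zero, so no claim about actual bias can be made. Confidence is high on the wording and low on the impact. This is a cheap improvement that does not put the design in doubt.

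**What to change.** 1. In Protocol 9.1.1.1 and 9.1.1.2, and in SAP 2.2.1, 2.2.2 and Appendix 3, define intercurrent event 1 as starting a prohibited medication or prohibited phototherapy or artificial UV.
2. In SAP Appendix 4, add a matching deviation sub-category, checked and dated against the procedure and non-drug treatment entries.
3. Update row 3 of SAP Table 4 so that these cases are counted.
4. State whether bleach baths count, and why.

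If the sponsor means to leave procedures out of the event, it should say so and give the reason.

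The cost is a small amount of estimand and SAP wording, which should be settled before unblinding. No new data are needed, because Protocol 6.9 already requires procedures to be recorded with reason and dates. A responder or two may become a non-responder. The change concerns scoring only and alters no rule on treatment, rescue or stopping.

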9.1.1.2. Secondary Estimands

Estimand (E2) strategy is defined for a continuous secondary endpoint at a visit (eg, percent change from baseline in EASI score at Week 16). The secondary estimand (E2) for continuous endpoints is defined by the following attributes:

- 1. Treatment condition: received study intervention of etrasimod 2 mg QD or placebo.
- 2. Population: Participants with moderate-to-severe AD as defined by inclusion and exclusion criteria.
- 3. Variables: Percent change from baseline in EASI total score at Week 16. If a participant in the etrasimod 2 mg QD group experiences the intercurrent event of initiation of prohibited medications or discontinuation of study treatment due to any reason (whichever is earlier), the endpoint data after the intercurrent event will be treated as missing and then imputed via multiple imputations as if they are in placebo group (ie, no treatment benefit).

4. Intercurrent events:

- A) Initiation of prohibited medications a participant who receives prohibited medications post-randomization prior to Week 16, the endpoint data after the intercurrent event will be treated as missing and then imputed via multiple imputation as if they are in placebo group (ie, no treatment benefit).
- B) Discontinuation of study intervention due to any reason prior to the Week 16 visit a participant who discontinues study treatment due to any reason, the endpoint data after the intercurrent event will be treated as missing and then imputed via multiple imputation as if they are in placebo group (ie, no treatment benefit).
- 5. Population-level summary: The mean difference in percent change from baseline in EASI score at Week 16 between etrasimod 2 mg QD and placebo.

Estimand E2 will also be applied to percent change from baseline in EASI score at visits prior to Week 16.

9.1.2. Multiplicity Adjustment

No multiplicity adjustment will be made in the study.

9.2. Analysis Sets

For purposes of analysis, the following analysis sets are defined:

Participant Analysis Set	Description
Full analysis set	All participants randomly assigned to study intervention, irrespective of whether they received any dose of study intervention. Participants will be analyzed in the treatment groups as they are randomized.
Safety analysis set	All participants randomly assigned to study intervention and who take at least 1 dose of study intervention. Participants will be analyzed according to the product they actually received.

9.3. Statistical Analyses

The SAP will be developed and finalized before any analyses are performed and will describe the analyses and procedures for accounting for missing, unused, and spurious data. This section is a summary of the planned statistical analyses of the primary and secondary endpoints.

9.3.1. General Considerations

The efficacy and safety data will be summarized by treatment group in Part 1. The Part 2 will be summarized separately. The efficacy endpoints will be summarized using descriptive statistics: the number and percent of participants for response-type endpoints, and with the number of participants, mean, standard deviation, median, minimum, and maximum for continuous endpoints.

9.3.2. Primary Endpoint Analysis

A landmark analysis of the IGA response endpoint at Week 16, defined in Section 9.1.1.1, will be performed in the FAS (among participants with baseline IGA \geq 2) using the Cochran-Mantel-Haenszel method adjusted for the actual randomization/stratification factor IGA score (3 [moderate AD], 4 [severe AD] based on clinical database) at Baseline using normal approximation for the difference in binomial proportions. The IGA response rate difference between the etrasimod group and the placebo group in the proportion of participants achieving (ie, IGA of clear (0) or almost clear (1) (on a 5-point scale) and a reduction of \geq 2 points from baseline at Week 16) along with its 95% confidence interval will be reported. Estimand E1 defined in Section 9.1.1.1 will be used. Any missing values after accounting for the intercurrent events will be considered as an IGA non-responder (ie, treatment failure).

